Study Title: Postoperative Hip Bracing After Hip Arthroscopy

Document Name: Study Protocol & Statistical Analysis Plan

Document Date:

NCT #: NCT04599296

PI Name: [name]

IRB approval date: 7/17/2020

RESEARCH PLAN

Abbreviations: FAIS – femoroacetabular impingement syndrome, IPT – iliopsoas tendonitis, NPRS – numerical pain ranking scale, HOOS-P – Hip disability and Osteoarthritis Outcome Score (Pain Subscale), PI – principal investigator

Global Hypothesis: Postoperative hip braces reduce patient pain and improve hip function after arthroscopic osteoplasty and labral repair for FAIS.

AIM 1, Primary goal: To test whether postoperative hip bracing affects patient NPRS scores in the first 6 weeks after arthroscopic surgery for FAIS. We will randomize 3-week continuous use of a postoperative hip brace (Fig 1) in patients who undergo arthroscopic surgery for FAIS. We will compare mean NPRS scores at the 3- and 6-week postoperative visit between groups. We hypothesize that at both time points, the Brace group will have lower mean NPRS scores compared to the No Brace group.

Figure 1

AIM 2, Secondary goals: To test whether postoperative hip bracing affects gait pattern, IPT symptoms, HOOS-P scores, or use of narcotic medication at 6 weeks after surgery. At the 6-week postoperative visit, a blinded investigator will assess patients for antalgic gait in clinic as well as for IPT signs through four established tests: 1) resisted seated hip flexion, 2) Stinchfield test, 3) psoas stretch test, and 4) hip flexor tenderness to palpation¹. We will compare the rate of the antalgic gait pattern and flexor symptoms between groups. We will compare patient reported HOOS-P scores and the rate of narcotic prescription refills between Brace and No Brace groups. We hypothesize that compared to the No Brace group, the Brace group will have a lower rate of IPT signs, lower rate of antalgic gait, better HOOS-P scores, and lower refill rate of narcotics at 6 weeks postoperatively.

AIM 3, Long term goals: To test whether postoperative hip bracing affects NPRS, HOOS-P scores, IPT symptoms, and use of pain medication at 6-months after surgery. Patients will be followed to determine if the short period of brace wear has lasting effects on recovery after hip

arthroscopy for FAIS. We will compare NPRS, IPT, and HOOS-P at 6 months after surgery. We will also compare between groups the rate of topical anti-inflammatory prescription or iliopsoas tendon/bursa cortisone injection within the 6-month postoperative period. We hypothesize that NPRS, IPT and HOOS-P scores will be the same between groups at 6 months postoperatively. We hypothesize that the No Brace group will have a higher rate of topical anti-inflammatory use and IP cortisone injection compared to the Brace group.

Background/Significance

Hip arthroscopy for treatment of FAIS involves reshaping of the osseous sources of impingement ("osteoplasty") and repair of impingement-associated labral tears. It is primarily done in patients under 50 years of age as a method of hip preservation. Diagnoses of FAIS and the incidence of hip arthroscopy have both increased dramatically in the last 20 years in the US^{2,3}. In our study using IBM Marketscan to evaluate rates of hip arthroscopic treatment of FAIS, we found this incidence doubled from 1.2 to 2.1 per 100,000 person-years in just a 3-year period⁴. During an arthroscopic procedure for FAIS, the hip joint is subluxated to allow for entry of camera and tools. Pain from muscle soreness from hip distraction is common in the immediate postoperative period⁵. Furthermore, the standard portals for hip arthroscopy enter near or through the hip abductor muscles (gluteus medius & minimus) and this process causes initial abductor inhibition⁶. Postoperatively, patients are at risk to overuse hip flexors in gait and develop IPT^{1,6}. Current postoperative hip arthroscopy rehabilitation is centered around muscle recovery and prevention of IPT⁷. Despite the increasing incidence of hip arthroscopy in the US, on a recent review we have found few evidence-based studies on postoperative care⁸.

A particular area of debate is the use of postoperative hip braces (**Fig 1**). A survey of 27 high-volume orthopaedic surgeons specializing in hip arthroscopy found that 59% used a postoperative hip brace for an average of 3.4 weeks⁹. Among 31 hip arthroscopy postoperative protocols available online, 55% used a brace for a median of 2 weeks¹⁰. A survey of 48 surgeons at an international hip arthroscopy conference found that 40% of "expert" surgeons (>500 career hip arthroscopies) used a postoperative brace¹¹. Postoperative hip braces are advocated to decrease postoperative pain by offloading hip musculature. They may also prevent overuse of the hip flexors by supporting the hip during gait. Additional cited benefits of postoperative hip braces include assisted normalization of gait in weight bearing¹⁰, protection of capsular closure⁷, and reduction in the risk of postoperative hip dislocation (which is low at 0.58%)¹². However there are no studies looking at efficacy of hip braces after hip arthroscopy⁸. The utility of bracing is important because hip braces are expensive (averaging \$350-\$600):

if there are over 7000 hip arthroscopies performed nationwide and 50% of surgeons use hip braces, this amounts to over \$2,000,000. We aim to test the cited benefits of postoperative hip bracing through NPRS pain scores, HOOS pain scores, use of pain medication, specific tests for IPT, and gait observation.

Approach

The proposed study design is an intent-to-treat, single-blind randomized controlled trial for treatment superiority. Inclusion criteria include any patient aged 14-60 at Husky Stadium Sports Medicine Center who is scheduled to undergo arthroscopic osteoplasty and labral repair for FAIS. We will exclude anyone who cannot follow up in our clinic for their 3- and 6-week postoperative visits. We will also exclude any patient with planned iliopsoas tendon release for tendonitis at the time of surgery. See **Fig 2** for flow chart of patient enrollment, treatment arms, and assessment.

The randomization sequence will be created in Excel with 1:1 allocation using random block sizes by an independent physician (co-investigator), and then assigned to patients in opaque, tamperproof envelopes with key stored in secure

[figure not shown]

Figure 2. Flow chart of study design

location by the co-investigator and unknown to the PI. The patients assigned to the Brace group will receive a standard postoperative hip brace at their preoperative visit with the Physician Assistant, billed to the Research Account (~\$290/brace). Patients in the Brace group will be expected to wear their braces at all times for the initial 3-week period except shower and toilet, as per current standard of care. Patients in both groups will be prescribed our standardized physical therapy protocol for arthroscopic hip osteoplasty and labral repair. All data will be stored in a de-identified, secure server maintained by the research coordinator and PI (REDcap). As all patients will have discontinued their braces by the 6-week visit this will be a single-blinded trial; the PI - who will be analyzing patient reported outcome measures and performing each exam at the 6-week visit - will have no knowledge of patient assignment. Any patient care questions will be managed by the Physician Assistant and nursing team so as to ensure no accidental exposure of the PI to a question about bracing.

Statistical Analysis, Feasibility, Safety: As short-term NPRS scores are absent in the literature for hip arthroscopy, sample size has been calculated using 2-years of pilot data on 6-week postoperative NPRS scores for FAIS patients (all wore braces) in the PI's practice, demonstrating a mean NPRS of 2.4 (SD 1.7). Given the cost of hip bracing, a treatment effect size of 50% increase in pain in the No Brace group (mean NPRS 1.2 higher) is used with 1:1 enrollment ratio and standard two-sided alpha of 0.05 and beta of 0.20,

resulting in a total of 32 patients per group. Assuming a 10% drop out this would be 36 patients per group. Baseline and postoperative data will be compared using Fisher exact test and *t* testing.

The PI is the only provider in the UWMC system who performs hip arthroscopy and in order to contain cost this will be a single-center study. The PI currently performs approximately 50-75 hip arthroscopies for FAIS per year. A pilot feasibility questionnaire was administered to 18 hip patients over a 3-month period with 17/18 (94%) responding favorably to participate in the trial. We expect high follow-up rates at 6 weeks as in the PI's current practice this rate is 94.7% among FAIS patients. We thus anticipate enrollment and 6-week results to be complete within 2 years, with pilot data within 1 year. During the study period we will monitor for any serious adverse effects including hip dislocation, revision surgery, or intractable pain. These will be promptly reported to the IRB and trial sponsor.

Strengths & Weaknesses: This study is innovative as there are no evidence-based reports on bracing after hip arthroscopy. This study is important because of the cost of bracing and frequency of hip arthroscopy. There is excellent equipoise as approximately 50% of surgeons use postoperative hip braces. This study also would add to its field by providing short term postoperative pain data as well as high quality data on incidence of IPT after hip arthroscopy. If the null hypothesis is shown and there are no differences between groups, we could justify disuse of hip braces and reduce societal costs. The most obvious weakness lies in the ability to recruit and meet sample size requirements. In case of poor enrollment, we will use

these data as an internal pilot study, to refine group variability/event rates and expand to a multicenter trial (the PI has already received interest from several academic centers that wish to participate), with hope for extramural funding.

References

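### The primary NPRS comparison is by t test at each visit with no provision for randomised patients who miss one, so uneven pain-related loss could bias it

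*Combined protocol and SAP*

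**What the plan says.** Aim 1 sets the primary comparison: "We will compare mean NPRS scores at the 3- and 6-week postoperative visit between groups". The Approach section gives the analysis principle: "The proposed study design is an intent-to-treat, single-blind randomized controlled trial for treatment superiority". The whole analysis method is one sentence under Statistical Analysis, Feasibility, Safety: "Baseline and postoperative data will be compared using Fisher exact test and" t testing.

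Loss to follow-up enters in two places in that section. The sample size is inflated from 32 per group: "Assuming a 10% drop out this would be 36 patients per group". For 6-week follow-up in the PI's current practice, "this rate is 94.7% among FAIS patients".

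The document does not define an analysis set. It gives no rule for missing NPRS scores, no imputation or repeated-measures model, no sensitivity analysis for missing data, and no reporting of loss by arm.

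**The concern.** A t test on week-6 scores can use only patients who have a week-6 score. Someone with a 3-week NPRS who misses week 6 contributes nothing to the 6-week comparison, although the 3-week score says something about the missing value. Raising the sample size restores numbers but does not make the remaining patients comparable between arms.

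If the No Brace patients in most pain are the ones who miss week 6, the apparent benefit of the brace shrinks. Strengths & Weaknesses says that a finding of no difference could justify giving up hip braces, so a shrunken difference matters here. If No Brace patients who are doing well skip the visit, the benefit is inflated instead. Without a prespecified rule, the handling of missing scores would be chosen after the data are seen.

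**Working it through.** **Inputs from the plan.** SD 1.7, target difference 1.2, two-sided alpha 0.05, power 80%, 36 randomised per group, 10% dropout allowed, 94.7% expected 6-week follow-up (5.3% loss).

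**Assumptions, because the plan gives no figure.** Loss by arm, how loss relates to pain, and a week-3/week-6 NPRS correlation ρ of 0.4 to 0.7.

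**1. The plan's sample size.** n = 2 × 1.7² × (1.960 + 0.842)² / 1.2² = 31.5, rounded up to 32. Then 32/0.9 = 35.6, rounded up to 36. Both figures reproduce. Expected losses are 72 × 0.10 = 7.2 patients at the allowed rate and 72 × 0.053 = 3.8 at the practice rate.

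**2. When bias arises.** Let m be the share missing in an arm, and s the amount by which the missing patients' mean NPRS exceeds the attenders' mean. The full-arm mean is the attenders' mean plus m × s. For the difference No Brace minus Brace,

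bias = (m × s in Brace) − (m × s in No Brace).

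This is zero if loss is unrelated to pain (s = 0), or if m and s are the same in both arms. With 5% lost in Brace, 15% in No Brace and s = 1.7 in both, it is 0.05 × 1.7 − 0.15 × 1.7 = −0.17 points.

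**3. One-sided selection on week-3 pain, by hand.** Let the k highest week-3 scores of 36 be lost in No Brace, with Brace losses random. The k highest of 36 standard normal values average about 1.64 for k = 4 and 1.91 for k = 2. The expected t-test estimate is 1.2 − [k/(36 − k)] × average × 1.7 × ρ.
- k = 4: (4/32) × 1.64 × 1.7 = 0.349. Estimate 1.2 − 0.349 × 0.4 = 1.06 at ρ = 0.4, and 1.2 − 0.349 × 0.7 = 0.96 at ρ = 0.7.
- k = 2: (2/34) × 1.91 × 1.7 = 0.191. Estimate 1.12 and 1.07.

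**4. Simulation of the week-6 comparison.** 36 per arm, true difference 1.2, the same number lost in each arm; ranges run over ρ = 0.4 to 0.7 and repeated runs. Two of 36 is 5.6% and four of 36 is 11.1%, close to the plan's 5.3% and 10%.

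| Loss pattern | Lost per arm | t-test estimate | Power |
|---|---|---|---|
| Random in both arms | 4 | about 1.20 | about 80% |
| Same worst-pain selection in both arms | 4 | 1.20 | 80% to 84% |
| No Brace, mild selection on high week-3 pain; Brace random | 2 | about 1.13 to 1.17 | about 78% to 79% |
| No Brace, highest week-3 pain; Brace random | 2 | about 1.07 to 1.13 | about 74% to 76% |
| No Brace, mild selection; Brace random | 4 | about 1.08 to 1.14 | about 71% to 75% |
| No Brace, highest week-3 pain; Brace random | 4 | about 0.95 to 1.07 | about 62% to 71% |
| No Brace, lowest week-3 pain; Brace random | 4 | 1.33 to 1.45 | not needed here |

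**5. What a model of both visits recovers.** When loss depends only on observed week-3 pain, a likelihood estimate using both visits averages about 1.20 in these patterns. When the four No Brace losses are those with the highest week-6 pain itself, it averages about 0.9 to 1.0, against about 0.85 for the t test. The model then corrects only part of the bias.

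**The case against.** The strongest reply is that expected loss is small and the harmful pattern is assumed. That stands. Nothing in the documents indicates that No Brace losses would be the patients in most pain while Brace losses are random. At close to the 5.3% loss rate with mild one-sided selection, the shift is only about 0.04 to 0.07 points. A repeated-measures model is also one acceptable choice among several.

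A reader might infer four stronger points that the documents do not support.

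- **That the t tests contradict the intent-to-treat label.** The label can mean analysis by assigned arm whatever brace wear occurred, and nothing in the plan departs from that. The gap is in who is included and how missing scores are treated. Nor is this a completers analysis in the strict sense, since each test uses the cases available at that visit.
- **That inflating 32 to 36 proves an attenders-only test.** Allowing for dropout is ordinary under any analysis. It shows that loss is expected, not how lost patients will be handled.
- **That the follow-up exclusion could remove patients after randomisation.** The sentence "We will exclude anyone who cannot follow up in our clinic for their 3- and 6-week postoperative visits" stands among the eligibility criteria beside a planned surgical procedure. It reads as an enrolment screen, and it should reduce loss.
- **That the 94.7% figure is uninformative.** It comes from the same practice at the same visit. The pilot NPRS patients all wore braces, but the plan does not say this of the follow-up cohort. How well the figure carries over to No Brace patients is uncertain, but it is still evidence.

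**Conclusion.** The point holds as an unaddressed missing-data problem in the primary analysis. Under the assumptions above (selection on high week-3 pain in No Brace only, random loss in Brace, ρ of 0.4 to 0.7), a true 1.2 is estimated at about 1.07 to 1.17 with 2 of 36 lost per arm. With 4 of 36 lost it is about 0.95 to 1.14, with power of about 62% to 75% against about 80% under random loss. The opposite selection biases upward. With random loss, or the same pain-related loss in both arms, there is no bias. The likely effect is therefore modest, but the plan has no means of detecting or limiting it, and a better method is cheap. It should be changed; it does not invalidate the design or the sample size.

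**What to change.** 1. In Statistical Analysis, Feasibility, Safety, state that all randomised patients with any postoperative NPRS are analysed by assigned arm in one likelihood-based repeated-measures model with arm, visit, arm by visit and an unstructured covariance. Take the 3- and 6-week differences from that model and keep the t tests as a sensitivity analysis.
2. Collect NPRS and HOOS-P by REDCap survey from anyone who misses a visit. Both are self-reported and REDCap already holds the trial data. The examined outcomes (gait and iliopsoas signs) cannot be recovered this way.
3. Report loss by arm, and add a shift (tipping-point) check: how much worse or better the missing patients' scores would have to be to change the conclusion. This is needed because the model does not fully correct loss that depends on unobserved week-6 pain, and it leaves out patients with no postoperative score.

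Cost: a few sentences of analysis plan, a survey link and slightly more analysis work, with no extra patients. The downside is that a few scores will come by survey rather than in clinic.

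### NPRS and HOOS-P appear to be compared by unadjusted t tests; prespecified adjustment for the baseline score could add precision at low cost

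*Combined protocol and SAP*

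**What the plan says.** The analysis method is given in a single sentence under Statistical Analysis, Feasibility, Safety: "Baseline and postoperative data will be compared using Fisher exact test and" t testing. It does not pair tests with outcomes. No ANCOVA, regression, mixed model or change-score analysis is mentioned anywhere.

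The aims describe plain between-group comparisons:

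- Aim 1 (primary): "We will compare mean NPRS scores at the 3- and 6-week postoperative visit between groups".
- Aim 2: "We will compare patient reported HOOS-P scores and the rate of narcotic prescription refills" between arms at 6 weeks.
- Aim 3: "We will compare NPRS, IPT, and HOOS-P at 6 months after surgery".

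The sample size uses the pilot 6-week NPRS (mean 2.4, SD 1.7), a difference of 1.2 points, two-sided alpha 0.05 and beta 0.20, and arrives at 32 per group. Then: "Assuming a 10% drop out this would be 36 patients per group". No correlation with baseline enters the calculation.

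The text refers to baseline data but does not say whether NPRS or HOOS-P is among them. The flow chart (Figure 2) is not available in the text reviewed, so whether these scores are collected before surgery cannot be judged.

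**The concern.** An unadjusted comparison of means is valid under randomisation, and it fits the stated intent-to-treat design. The issue is efficiency. If a patient's preoperative pain score predicts part of the later score, a t test leaves that variation in the error term and ANCOVA removes it.

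Precision gained without more patients is useful here. The trial relies on one surgeon with about 50 to 75 eligible operations a year, and Strengths & Weaknesses says: "The most obvious weakness lies in the ability to recruit and meet sample size requirements". The same section says that a finding of no difference could justify abandoning braces, and that conclusion depends on how narrow the confidence interval is.

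The choice needs to be made in advance. A covariate added after the data are seen is open to the charge that it was picked for its result.

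**Working it through.** **Inputs from the plan** (Statistical Analysis, Feasibility, Safety): SD 1.7, difference 1.2, two-sided alpha 0.05, power 80%, 1:1 allocation, 32 per group before dropout and 36 after. Expected 6-week follow-up: "current practice this rate is 94.7% among FAIS patients".

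**Assumed input:** the correlation r between baseline and 6-week NPRS, which the documents do not give. Values of 0, 0.1, 0.2, 0.3 and 0.5 are shown.

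**Step 1. Reproduce the plan's figure.** By the normal approximation, n per group = 2 × [1.7 × (1.960 + 0.842) / 1.2]² = 31.5, rounded up to 32. The exact t calculation gives 32.5, so 32 per group has 79.4% power by t test (80.6% by the normal approximation). Dropout: 32 / 0.9 = 35.6, rounded up to 36. The plan's figures reproduce as an unadjusted two-group comparison of means.

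**Step 2. Unadjusted precision.** Half-width of the 95% CI = t(0.975, 2n − 2) × 1.7 × √(2/n).

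- n = 32: 1.999 × 1.7 × 0.25 = 0.85 points.
- n = 34 (36 × 0.947 = 34.1): 1.997 × 1.7 × 0.2425 = 0.82 points, with 81.8% power.

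**Step 3. Adjusted precision.** The residual SD becomes 1.7 × √(1 − r²): 1.67 at r = 0.2, 1.62 at 0.3 and 1.47 at 0.5. ANCOVA also has a price: one degree of freedom (2n − 3), and a variance factor 1 + F/(2n − 2) for chance baseline imbalance, where F follows an F distribution on 1 and 2n − 2 degrees of freedom. Power (noncentral t) and half-width are averaged over that factor.

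| r (assumed) | Power, n = 32 | Half-width, n = 32 | Power, n = 34 | Half-width, n = 34 |
|---|---|---|---|---|
| t test | 79.4% | 0.85 | 81.8% | 0.82 |
| 0 | 78.7% | 0.86 | 81.2% | 0.83 |
| 0.1 | 79.1% | 0.85 | 81.6% | 0.83 |
| 0.2 | 80.3% | 0.84 | 82.7% | 0.81 |
| 0.3 | 82.4% | 0.82 | 84.7% | 0.79 |
| 0.5 | 88.9% | 0.74 | 90.7% | 0.72 |

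The two methods have equal power at r = 0.130 (n = 32) and r = 0.126 (n = 34).

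**Step 4. Express the gain in patients.** The t-test sample size per arm with the same power as ANCOVA at 32 per arm is 32.7, 34.5 and 41.6 at r = 0.2, 0.3 and 0.5. The gain is therefore about 0.7, 2.5 and 9.6 patients per arm.

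**Step 5. What it does for a null result.** At n = 34 the half-width is 0.82 / 2.4 = 34% of the pilot mean unadjusted, and 34%, 33% and 30% adjusted at r = 0.2, 0.3 and 0.5. Adjustment does not settle what a null result could rule out.

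**Step 6. Checks.** Simulation of 60,000 trials per setting gave ANCOVA power of 80.2, 82.3 and 89.0% at n = 32, and 82.9, 84.6 and 90.8% at n = 34, in line with the table. With an assumed 10% of baseline scores missing and filled with the overall mean (40,000 trials), power was 80.3, 81.9 and 88.1% at n = 32, and 82.3, 84.3 and 89.9% at n = 34.

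None of this can be sized for NPRS at 3 weeks or 6 months, or for HOOS-P, because the documents give no SD for them.

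**The case against.** The strongest reply is that nothing is broken. The t test is valid, the sample size agrees with it, and at 34 per group unadjusted power is already 81.8%, above the 80% target. The benefit rests on a correlation that the documents do not supply. Surgery falls between the two scores, and the Background attributes much early pain to the procedure itself, so the correlation could be low. At 0.1 adjustment slightly loses power (79.1% against 79.4% at 32 per group), and at 0.2 it is worth less than one patient per arm. Only 0.5 brings a clear gain, and no figure in the plan supports that value. If baseline scores are not collected, data collection is needed as well as analysis text. The plan also has a fallback for poor enrolment: use the data as an internal pilot and go multicentre.

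All of this stands as a limit on size, and it is why the point is only an option. It does not reverse the balance: the worst case costs about 0.7 power points, while r = 0.5 would gain about 9.5 (88.9 − 79.4).

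It is also fair to say that the unadjusted reading is inferred from a terse sentence. That sentence could mean balance tests at baseline or before-and-after comparisons, but no reading of it includes baseline adjustment.

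Two further remarks have merit and are taken up in the fix: a prespecification should settle on one model, and the plan does not say when the allocation envelope is opened relative to the preoperative visit.

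**Conclusion.** The point holds as an optional improvement. The plan names no baseline adjustment, its unadjusted analysis is valid, and adjustment could add precision at little cost. For 6-week NPRS at 32 per group, the gain is about 1 to 3 power points at an assumed correlation of 0.2 to 0.3 and about 9.5 points at 0.5. There is no gain below about 0.13 and a loss of about 0.7 points at zero. These figures rest on the pilot SD of 1.7 applying to both arms and on the assumed correlations. Confidence is medium, because the correlation is unknown and the text does not show whether baseline NPRS or HOOS-P is recorded.

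**What to change.** Add to Statistical Analysis, Feasibility, Safety:

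- **NPRS.** Analyse the score at 3 weeks, 6 weeks and 6 months by assigned arm, using ANCOVA on baseline NPRS at each visit, and report the adjusted difference with its 95% CI. A mixed model with arm, visit, arm-by-visit and baseline NPRS, reporting the contrast at each visit, is an acceptable alternative. Name one of the two in advance.
- **HOOS-P.** At 6 weeks and 6 months, use ANCOVA on baseline HOOS-P if it is collected. If it is not, either add the pain subscale at the preoperative visit or adjust for baseline NPRS, and state which.
- **Timing of the baseline score.** If baseline NPRS is not already recorded, ask for it at the preoperative visit before allocation is revealed. Brace patients "receive a standard postoperative hip brace at their preoperative visit", so the order within that visit matters and should be written down, including when the envelope is opened.
- **Missing data.** Fill a missing baseline score with the mean over both arms, so that no patient is dropped for that reason. State the assumption made about missing postoperative scores: the mixed model assumes missing at random, and ANCOVA on observed scores needs a stated assumption too.
- **Baseline comparisons.** If the existing sentence means significance tests between arms at baseline, replace them with a description by arm.

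The cost is a few lines of text and code. If baseline scores are not yet collected, add one NPRS question, plus the short HOOS pain subscale unless baseline NPRS serves as its covariate, at a visit already planned. The downsides are a small gain if the correlation is low, a loss of up to about 0.7 power points if it is zero, and no help from patients with no postoperative score.

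### Fisher's exact test is valid but conservative for the binary outcomes of Aims 2 and 3; a precisely defined Boschloo test stays within 5%, is never less powerful, and may add about 0 to 13 points of power

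*Combined protocol and SAP*

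**What the plan says.** The paragraph on statistical analysis, feasibility and safety, in the Approach section, gives the whole analysis in one sentence: "Baseline and postoperative data will be compared using Fisher exact test and" t testing. It does not say which test goes with which outcome. The natural reading is Fisher for rates and t for scores.

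The rates are in Aims 2 and 3. At 6 weeks, "We will compare the rate of the antalgic gait pattern and flexor symptoms between groups", together with narcotic refills. At 6 months, IPT signs again and "the rate of topical anti-inflammatory prescription or iliopsoas tendon/bursa cortisone injection within the 6-month postoperative period". No event rate or power is given for any of them.

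The sample size rests on NPRS alone: pilot data "demonstrating a mean NPRS of 2.4 (SD 1.7"), a "50% increase in pain in the No Brace group (mean NPRS 1.2 higher"), and "standard two-sided alpha of 0.05 and beta of 0.20", "resulting in a total of 32 patients per group". With 10% dropout this becomes 36 per group.

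**The concern.** Fisher's test conditions on the total number of events. With about 30 to 36 patients per arm, few distinct p-values are possible, so the test usually cannot come close to using its nominal 5%. Unused type I error is lost power.

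This matters here for two reasons. Three of the four Aim 2 outcomes are rates, and their power is whatever a trial sized for NPRS happens to give. The strengths and weaknesses paragraph also says that finding no difference could justify giving up braces, so non-significant results may be acted on. If an equally valid test has more power at the same nominal level, the plan could name it at almost no cost.

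**Working it through.** **Inputs from the plan.** NPRS SD 1.7; difference 1.2; two-sided alpha 0.05; beta 0.20; "1:1 allocation using random block sizes"; 32 evaluable and 36 enrolled per group.

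**Assumptions.** The 5% two-sided level is stated for NPRS and is carried over to the binary outcomes. All event rates are assumed and shown as ranges.

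**The plan's own figure.** n = 2 × (1.7/1.2)² × (1.960 + 0.842)² = 31.5, so 32 per group; 32/0.90 = 35.6, so 36. Both reproduce. The t-based version gives 32.5, so 33, which is immaterial.

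**Method for the binary outcomes.** All 2×2 tables were enumerated under two independent binomials.
- Size at common rate p = Σ Pr(x | n₁, p) Pr(y | n₂, p) over the rejected tables. Power is the same sum with different rates in the two arms.
- Fisher rejects when its two-sided p ≤ 0.05.
- Boschloo uses that same two-sided Fisher p as its statistic. The cutoff is raised as far as possible while the maximum size over the common rate (grid of 1,999 values) stays ≤ 0.05. Its rejection region therefore contains Fisher's.

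**Fisher's true size, equal arms**

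| Event rate | 32/32 | 34/34 | 36/36 |
|---|---|---|---|
| 10% | 1.1% | 1.2% | 1.4% |
| 20% | 2.4% | 2.4% | 2.6% |
| 30% | 2.8% | 2.7% | 2.8% |
| 50% | 3.3% | 2.6% | 2.5% |

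At a 5% event rate it is 0.2 to 0.3%.

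**Fisher's true size, unequal arms, rates 10 to 90%.** 31/33: 2.4 to 4.1%. 30/34: 2.8 to 4.2%. 33/35: 2.0 to 3.8%. 35/36: 2.3 to 3.7%.

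**Boschloo's maximum size.** 4.67% at 32/32, 4.66% at 34/34, 4.94% at 36/36, and at most 5.0% at the unequal splits.

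**Power, Fisher to Boschloo** (the first arm has the lower rate)

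| Arms | Rates | Fisher | Boschloo | Gain (points) |
|---|---|---|---|---|
| 32/32 | 10% v 30% | 41.1% | 48.5% | 7.5 |
| 32/32 | 30% v 70% | 87.9% | 88.7% | 0.9 |
| 34/34 | 10% v 30% | 43.8% | 52.4% | 8.6 |
| 34/34 | 20% v 50% | 67.9% | 74.1% | 6.2 |
| 36/36 | 5% v 20% | 34.5% | 47.1% | 12.6 |
| 36/36 | 30% v 60% | 63.6% | 72.2% | 8.6 |
| 33/35 | 10% v 30% | 48.6% | 50.5% | 2.0 |
| 30/34 | 30% v 60% | 66.4% | 66.7% | 0.3 |

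Gains come from unrounded powers, so they can differ by 0.1 from the columns shown.

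**One table.** With 4/34 v 11/34, Fisher gives p = 0.077 and Boschloo p = 0.047.

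**The version matters.** Some software (SciPy, for example) doubles the smaller one-sided Boschloo p-value. With unequal arms that version can miss tables that Fisher rejects: 2/34 v 8/33 gives Fisher 0.045 and doubled Boschloo 0.0502. At 34/33 with 5% v 20%, its power is 37.3% against 41.0% for Fisher.

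**The case against.** The strongest reply is that nothing here is wrong. Fisher's test controls type I error and is conventional at this size, so the choice among exact tests is one of efficiency. That stands.

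A reader might infer that every binary outcome loses several points of power. The documents do not support this. They give no event rates, and random blocks with some dropout do not guarantee equal evaluable arms. An imbalance of a few patients raises Fisher's size to as much as about 4%, and in some scenarios the gain falls to nearly nothing. It is also small where power is already high or events are very rare.

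A reader might also infer that the change carries no error cost. That is true only against the nominal 5%. Actual type I error rises, for example from 2.7% to about 4.7% at 34/34 and a 30% rate. The plan describes no multiplicity adjustment for these outcomes, so Fisher's conservatism gives some incidental protection. That protection varies with event rates and arm sizes and was not designed, so it is a weak reason to keep the test, but the cost is real.

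Finally, the swap does not make a non-significant result evidence of no difference. Power can stay below 80% with either test, as in every row of the power table except 30% v 70%. The risk difference and its interval answer that misreading better, and they can be reported whichever test is used.

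**Conclusion.** The point holds as an optional efficiency gain for secondary and long-term outcomes. It is not an error in the plan. At 32 to 36 per group Fisher's true size is about 1 to 3% with equal arms and event rates of 10 to 50%, about 2 to 4% with slightly unequal arms, and below 1% for rare events in equal arms. Boschloo's test with the two-sided Fisher p-value as statistic keeps size at or below 5% and never has less power. Its gain is about 0 to 13 points.

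The size of the gain rests on assumed event rates, on the final evaluable numbers, and on applying the 5% two-sided level to these outcomes. That the test never loses power follows from nested rejection regions and needs no assumed rates, but it applies only to this version. The NPRS comparison and the sample size are unaffected.

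**What to change.** In the statistical analysis paragraph, for the postoperative binary outcomes of Aims 2 and 3, replace Fisher's test with wording such as: *Binary outcomes will be compared with the two-sided Boschloo exact test at the 5% level, using the two-sided Fisher p-value as the test statistic and maximising over the common event rate; the doubled one-sided version will not be used. Each risk difference will be reported with a 95% score-type confidence interval.*

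The change should be made before outcome data are seen by group. It needs no new data and no more patients. The costs are a test less familiar to clinical readers, the need to check that the chosen software computes the stated version, and actual type I error closer to 5%. If the sponsor prefers to keep Fisher, the risk differences and intervals are still worth adding.
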